4.4.10.5 Withdrawal from the Roche Clinical Repository

Patients who give consent to provide RCR specimens have the right to withdraw their specimens from the RCR at any time for any reason. If a patient wishes to withdraw consent to the testing of his or her specimens, the investigator must inform the Medical Monitor in writing of the patient's wishes through use of the RCR Patient Withdrawal Form and, if the trial is ongoing, must enter the date of withdrawal on the RCR Research Sample Withdrawal of Informed Consent eCRF. The patient will be provided with instructions on how to withdraw consent after the trial is closed. A patient's withdrawal from Study GA30067 does not, by itself, constitute withdrawal of specimens from the RCR. Likewise, a patient's withdrawal from the RCR does not constitute withdrawal from Study GA30067.

4.4.10.6 Monitoring and Oversight

RCR specimens will be tracked in a manner consistent with Good Clinical Practice by a quality-controlled, auditable, and appropriately validated laboratory information management system, to ensure compliance with data confidentiality as well as adherence to authorized use of specimens as specified in this protocol and in the Informed Consent Form. Roche monitors and auditors will have direct access to

appropriate parts of records relating to patient participation in the RCR for the purposes of verifying the data provided to Roche. The site will permit monitoring, audits, IRB/EC review, and health authority inspections by providing direct access to source data and documents related to the RCR samples.

4.4.11 Assessments at Unscheduled Visits

An unscheduled visit may occur at any time during the study (i.e., due to flare of disease activity or due to an adverse event). Patients who are seen by the investigator or site staff at a timepoint not required by the protocol may undergo any of the assessments indicated (see Appendix 1), based on the reason for the unscheduled visit. These assessments may include collection of PK and PD, to assess drug exposure and/or PD measures of drug activity.

4.5 PATIENT, TREATMENT, STUDY, AND SITE DISCONTINUATION

4.5.1 Patient Discontinuation

Patients have the right to voluntarily withdraw from the study at any time for any reason. In addition, the investigator has the right to withdraw a patient from the study at any time. Reasons for withdrawal from the study may include but are not limited to the following:

- Patient withdrawal of consent at any time
- Any medical condition that the investigator or Sponsor determines may jeopardize
 the patient's safety if he or she continues in the study
- Investigator or Sponsor determines it is in the best interest of the patient
- Patient non-compliance, as per Principal Investigator's discretion

Every effort should be made to obtain information on patients who withdraw from the study. The primary reason for withdrawal from the study should be documented on the appropriate eCRF. However, patients will not be followed for any reason after consent has been withdrawn. Patients who withdraw from the study will not be replaced.

If a patient discontinues the study prior to the Week 52 treatment completion visit, an early termination visit should be conducted. These patients should return for the 8-week safety follow-up visit in this study (see Appendix 1).

Patients who discontinue the study during the safety follow-up period but prior to completion of the 8-week safety follow-up will be asked to return to the clinic within 30 days (± 7 days) after the last dose of study drug or last scheduled visit for an early termination visit (see Appendix 1).

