4.5.2 Study Treatment Discontinuation

Patients must discontinue study treatment if they experience any of the following:

- Pregnancy
- Anaphylaxis or other severe hypersensitivity reaction

- Malignancy (with the exception of non-serious local and resectable basal or squamous cell carcinoma of the skin)
- Any serious infection or infection requiring treatment with an IV antimicrobial agent
- Any prohibited medication as defined in Section 4.3
- Any Grade 3 or greater thrombocytopenia (National Cancer Institute Common Terminology Criteria for Adverse Events [NCI CTCAE v4.0])
- Any Grade 4 neutropenia (NCI CTCAE v4.0)
- Failure to achieve a 20% improvement in both SJC and TJC (relative to baseline values in Study GA29350) at Week 24

Patients who discontinue study treatment prematurely for the reasons listed above will be asked to return to the clinic for an early termination visit (see Section 4.5.1) followed by 8 weeks of safety follow-up.

The primary reason for study treatment discontinuation should be documented on the appropriate eCRF. Patients who discontinue study treatment prematurely will not be replaced.

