5. ASSESSMENT OF SAFETY

5.1 SAFETY PLAN

The safety plan for patients in this study is based on nonclinical and clinical experience with GDC-0853 in completed and ongoing studies as well as published literature on

GDC-0853—Genentech, Inc.

other BTK inhibitors. The important potential safety risks for GDC-0853 are outlined below. Please refer to the GDC-0853 Investigator's Brochure for a complete summary of safety information.

Several measures will be taken to ensure the safety of the patients participating in this study. Eligibility criteria in both the controlled and open-label studies have been designed to exclude patients at a higher risk for potential toxicities. Patients will undergo safety monitoring during the study, including monitoring of vital signs, physical examination, ECGs, and routine laboratory safety assessments (hematology, chemistry, and urinalysis) and assessment of the nature, frequency, and severity of adverse events. In addition, guidelines for managing potential adverse events, including criteria for treatment interruption or discontinuation, dose reduction, and enhanced safety reporting are provided below.

Dose reduction from 200 mg BID to 200 mg QD for safety events is permitted for specific events as detailed in Table 3 of Section 5.1.2. For adverse events not listed in the table where the investigator thinks a dose reduction may be indicated, please consult with the Medical Monitor.

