5.1.1.8 Vascular Inflammation

Vascular inflammation (vasculitis) was observed in dogs administered GDC-0853 at \geq 10 mg/kg/day (\geq 56 μ M • h) in the 4-week toxicity study, and these changes were not completely reversed by the end of the 4-week recovery period. There was no consistent correlation with any clinical biomarkers. However, in the 9-month toxicity study in dogs, no GDC-0853-related vascular inflammation was observed up to the highest dose of 10 mg/kg/day (36 μ M •h), which is considered to be the NOAEL (AUC) for the canine vascular inflammation findings.

The translatability of

these findings to humans is unknown; however, Beagle dogs are susceptible to spontaneous development of polyarteritis syndrome (Snyder et al. 1995) and may be more sensitive to any drug-induced effects. Further, there are several examples of approved therapies for which there is no correlation between the finding of vasculitis in dogs or rats at clinically relevant exposures and adverse outcomes in patients (FDA 2011).

As a safety risk-mitigation measure, patients with a history of vasculitis, including RA-associated vasculitis, will be excluded from the study, and CBC, creatinine, and urinalysis will be monitored in all patients during the study. Study drug should be discontinued in any patient who develops an adverse event of vasculitis, and the patient should enter safety follow-up.

Guidelines for management of GDC-0853 in the event of vasculitis in patients are provided in Table 3. Please refer to the GDC-0853 Investigator's Brochure for further details.

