combination with total bilirubin >2 × ULN, of which at least 35% is direct bilirubin, or clinical jaundice	Report event as adverse event of special interest to the Sponsor in an expedited manner.
Any AST or ALT $> 5 \times ULN$	Discontinue GDC-0853.
	Elevations of AST or ALT of $> 5 \times ULN$ should be reported as adverse event(s) of special interest to the Sponsor in an expedited manner.
Cardiovascular effects	
Sustained (at least two ECG measurements > 30 minutes apart) QTcF that is > 500 msec and/or > 60 msec longer than the baseline value	Unless there is a clear alternative cause other than study drug, discontinue GDC-0853 ^e

Table 3 Guidelines for Management of GDC-0853 in Patients Who Experience Specific Adverse Events (cont.)

Event	Action to Be Taken ^a
Sustained absolute QTcF that is > 515 msec	Unless there is a clear alternative cause other than study drug, discontinue GDC-0853 ^e
An episode of torsades de pointes or a new ECG finding of clinical concern	Unless there is a clear alternative cause other than study drug, discontinue GDC-0853 ^e
Vascular Inflammation	
Vasculitis	Consult with the Medical Monitor
Hypersensitivity reactions	
Fever, chills, pruritis, urticaria, angioedema, and skin rash	Treat patient according to the standard of care for management of anaphylaxis/anaphylactoid or a hypersensitivity reaction.
Cardiopulmonary reactions, including chest pain, dyspnea, hypotension, or hypertension	Discontinue GDC-0853.
Persistent gastrointestinal symptoms (e.g., crampy abdominal pain, vomiting)	

CBC = complete blood count; IV = intravenous; MTX = methotrexate; PLT = platelet count; ULN = upper limit of normal.

- ^a Any patient who discontinues GDC-0853 should enter safety follow-up if possible.
- b Appropriate laboratory investigations, including but not limited to cultures, should be performed to establish the etiology of any serious infection.
- ^c Patients withdrawn from the study because of a reduced neutrophil count must be followed closely for signs of infection, with treatment as deemed appropriate by the investigator, including discontinuation of MTX if indicated, and must have a repeat WBC count with differential performed weekly until the ANC is above 1000 cells/mm³ (1.0 × 10⁹/L) within 2 months (or sooner if deemed necessary by the investigator), a hematology referral is recommended.

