- Patients withdrawn from the study because of a reduced platelet count must have a repeat platelet count weekly until the count is above 100,000 cells/mm³ (100×10⁹/L); additional management and treatment should be as deemed appropriate by the investigator, including discontinuation of MTX if indicated. If the platelets do not return to above 100,000 cells/mm³ (100×10⁹/L) within 2 months (or sooner if deemed necessary by the investigator), a hematology referral is recommended.
- In rare circumstances, it may be acceptable to resume GDC-0853, provided that any ECG abnormalities have resolved and that the patient is appropriately monitored. Clinical judgment should be applied and discussion with the Medical Monitor should occur.

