Appendix 1 Schedule of Assessments

							Treat	ment V	isits								
Week	0 ^a	4	8	12	16 ^b	20 ^b	24	28 ^b	32 ^b	36	40 ^b	44 ^b	48 ^b	52	SC/		
Day (±days)	1 °	28 (±4)	56 (±4)	84 (±4)	112 (±3)	140 (±3)	168 (±7)	196 (±7)	224 (±7)	252 (±7)	280 (±7)	308 (±7)	336 (±7)	365 (±7)	SFU ^d (±7)	ET	UV e
Informed consent ^f	Х																
General medical history and baseline conditions	Х																
Inclusion/exclusion criteria	Х																
Concomitant medications	x ^g	Х	Х	х			Х			Х				Х	х	Х	Х
Adverse events	x ^g	Х	Х	х			Х			Х				Х	х	Х	Х
Vital signs ^h	x ^g	Х	Х	х			Х			Х				Х	х	Х	Х
Weight	x ^g														х	Х	
Complete physical examination i	x ^g																
Limited physical examination ^j		Х	Х	х			Х			Х				Х	х	Х	Х
ECG ^k	x ^g	Х	Х	х			Х			Х				Х	х	Х	Х
GDC-0853 administration in clinic	X m	Х	Х	х													
Hematology ⁿ	x ^g	Х	Х	х			Х			Х				Х	х		Х
Chemistry °	x ^g	Х	Х	х			Х			Х				Х	х		Х
Coagulation studies PT/PTT																	Х
Pregnancy test (urine) women ^p	x ^g	Х	Х	х	Х	Х	Х	Х	Х	Х	Х	Х	Х	Х	х	Х	Х
Drug dispensing	х	х	х	х	х	х	x	х	х	х	x	х	x				
Urinalysis ^q	х ^g	Х	Х	Х			Х			Х				Х	Х	Х	Х
Quantitative Ig ^r	x ^g			Х			Х			Х				Х			Х
Lipid panel ^s				Х											Х	Х	
Rheumatoid Factor/anti-CCP				х											х		

GDC-0853—Genentech, Inc. 109/Protocol GA30067, Version 2

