Appendix 1 Schedule of Assessments (cont.)

		Treatment Visits															
Week	0 ^a	4	8	12	16 ^b	20 b	24	28 ^b	32 ^b	36	40 ^b	44 ^b	48 ^b	52	SC/		
Day (±days)	1 °	28 (±4)	56 (±4)	84 (±4)	112 (±3)	140 (±3)	168 (±7)	196 (±7)	224 (±7)	252 (±7)	280 (±7)	308 (±7)	336 (±7)	365 (±7)	SFU ^d (±7)	ET	UV ^e
TBNK	x ^g			х			Х							Х	х	Х	Х
ACR/DAS:																	
CRP	x ^g	Х	х	х			Х			Х				Χ	х	Х	Х
ESR (on site or at local laboratory)	x ^g	х	х	х			х			х				х	х	Х	х
Tender/painful joint count (68), swollen joint count (66)	x ^g	х	х	X t			X ^t			х				х	х	х	х
Patient's Assessment of Arthritis Pain (VAS) ^u	x ^g	х	х	х			Х			х				х	х	х	х
Patient Global Assessment of Arthritis (VAS) ^u	x ^g	х	х	х			Х			х				х	х	х	х
Physician's Global Assessment of Arthritis (VAS) ^v	x ^g	х	х	х			Х			х				х	х	х	х
HAQ-DI ^u	x ^g	х	х	Х			х			х				Х	Х	х	х
SF-36v2 ^u	x ^g			Х			Х							Х	Х		
FACIT-Fatigue Scale ^u	x ^g			Х			Х							Х	Х		
Blood for PK assessment ×	x ^g			Х										Х		Х	х
PBMC protein lysate ^u (U.S. sites only)	x ^g			х										х	х		
Blood for FACS (U.S. sites only) w	x ^g			Х										Х	x		
Serum biomarkers	X ^g , x			x ^x										Х	х		
Plasma biomarkers	x ^g , x			X x			-		_					Х	x		

GDC-0853—Genentech, Inc. 110/Protocol GA30067, Version 2

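### Hematology and chemistry are not scheduled at the early termination visit, so many early leavers have no blood count or liver and renal chemistry at the time of stopping

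*Combined protocol and SAP*

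**What the plan says.** Section 4.5.1 covers patients who leave before Week 52: "If a patient discontinues the study prior to the Week 52 treatment completion visit, an early termination visit should be conducted". They should also return for the 8-week safety follow-up. Section 4.5.2 lists eight reasons for stopping treatment and says that these patients "will be asked to return to the clinic for an early termination visit (see Section 4.5.1) followed by 8 weeks of safety follow-up". Both routes lead to the ET column of Appendix 1.

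In Appendix 1, Hematology and Chemistry are marked at Weeks 0, 4, 8, 12, 24, 36 and 52, at safety follow-up and at unscheduled visits. Their ET cells are empty.

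Other parts of the protocol treat these tests as core monitoring. Section 5.1 refers to "routine laboratory safety assessments (hematology, chemistry, and urinalysis") as part of safety monitoring. Section 5.1.1.8 says that "CBC, creatinine, and urinalysis will be monitored in all patients during the study". Section 5.1.1.6 describes routine transaminase and bilirubin checks throughout. Table 1 includes changes in laboratory results, during and after administration, in the primary safety endpoints.

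**The concern.** The ET visit is the one visit tied to leaving early, and some patients leave because of a safety problem. Of the three tests that Section 5.1 groups together, only urinalysis is scheduled there. If no panel is drawn, the laboratory record of such a patient jumps from the last routine visit to a sample 8 weeks after the last dose. A change that arose before stopping and resolved off drug would not appear in the laboratory summaries of Section 6.4. The study is descriptive, so no test or power figure is affected. What is at stake is the completeness of a primary safety endpoint in the patients who stop.

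**Working it through.** The plan states no figure for this, so there is none to reproduce. The check reads the schedule row by row and then measures the gaps.

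**Step 1: the ET column.** Each row below has its full 17 visit cells, and neighbouring rows show ET marks. An extraction fault is therefore an unlikely explanation for the blanks.

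| Row | Treatment weeks marked | Follow-up | ET | Unscheduled |
|---|---|---|---|---|
| Hematology | 0, 4, 8, 12, 24, 36, 52 | yes | **no** | yes |
| Chemistry | 0, 4, 8, 12, 24, 36, 52 | yes | **no** | yes |
| Urinalysis | 0, 4, 8, 12, 24, 36, 52 | yes | yes | yes |
| CRP | 0, 4, 8, 12, 24, 36, 52 | yes | yes | yes |
| TBNK | 0, 12, 24, 52 | yes | yes | yes |
| Lipid panel | 12 | yes | yes | no |
| PK | 0, 12, 52 | no | yes | yes |

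Blood is already drawn at ET for CRP, TBNK, lipids and PK.

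**Step 2: who is covered some other way.**
- Stops for low neutrophils or platelets start from a blood count. Table 3 then adds weekly repeats; for example, "Patients withdrawn from the study because of a reduced platelet count must have a repeat platelet count weekly".
- Table 3 stops for raised transaminases start from a chemistry result.
- Week 24 efficacy stops fall at a visit with both panels.
- For serious infection, a Table 3 footnote says: "Appropriate laboratory investigations, including but not limited to cultures, should be performed to establish the etiology of any serious infection". It names no hematology or chemistry panel.
- Stops for pregnancy, hypersensitivity, malignancy or prohibited medication, and voluntary withdrawals, bring no specified panel.

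**Step 3: age of the last scheduled value.** Inputs are the nominal days in Appendix 1 (1, 28, 56, 84, 168, 252, 365) and follow-up 8 weeks (56 days) after the last dose. The worst case is a stop one day before the next visit:

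- oldest last value = (next visit day − 1) − last visit day
- gap to follow-up value = oldest last value + 56

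| Interval (days) | Oldest last value | Gap to follow-up value |
|---|---|---|
| 1 to 28 | 27 − 1 = 26 days | 26 + 56 = 82 days (11.7 weeks) |
| 28 to 56, 56 to 84 | 27 days | 27 + 56 = 83 days (11.9 weeks) |
| 84 to 168, 168 to 252 | 83 days | 83 + 56 = 139 days (19.9 weeks) |
| 252 to 365 | 364 − 252 = 112 days | 112 + 56 = 168 days (24.0 weeks) |

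Visit windows (±3 to ±7 days) are ignored and can lengthen or shorten these gaps.

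**Step 4: leaving during follow-up.** Section 4.5.1 asks patients who leave during safety follow-up to attend an ET visit within 30 days (±7) of the last dose or last scheduled visit. A patient who attends only that visit has no scheduled hematology or chemistry after treatment.

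**Step 5: effect of the fix.** With both panels at ET, and ET held at the time of stopping, the longest gap to the next scheduled draw falls from 139 to 83 days between Weeks 12 and 36. Between Weeks 36 and 52 it falls from 168 to 112 days.

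**The case against.** The strongest reply is that ET is a reduced visit by design. Quantitative immunoglobulins, SF-36v2, FACIT-Fatigue and the serum biomarkers are blank there too, and no text promises hematology or chemistry at ET. Unscheduled visits for adverse events may include both panels, the 8-week follow-up includes them, and Table 3 laboratory stops bring their own result. Section 4.5.1 also ends follow-up once consent is withdrawn, so some leavers are out of reach whatever Appendix 1 says.

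Much of this stands, and it limits the size of the point. A reader might infer that early leavers have no laboratory monitoring; the documents do not support that. But unscheduled panels depend on the reason for the visit, the follow-up sample comes 8 weeks after the last dose, and the laboratory-triggered stops are only some of the stops. None of this explains why urinalysis is kept at ET while the two panels grouped with it are not.

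A reader might also infer that safety and PD change must be measured from Day 84 of GA29350, and so from an on-drug value in patients from GDC-0853 arms. The text does not go that far. The Section 4.4 list of Day 84 baseline assessments also contains joint counts and HAQ-DI, which Table 1 analyses against the GA29350 baseline. Being on that list therefore does not fix the analysis reference. Section 6.7 requires a predose biomarker value without saying before which dose, and Section 6.4 already separates safety by parent-study treatment cohort. The supportable statement is that the reference is not specified. Nor is there a demonstrated conflict over the baseline for QTcF: Section 4.4 lists ECGs among the Day 84 assessments, and the QTcF passages do not contradict it.

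**Conclusion.** The schedule gap is real. Hematology and chemistry are not scheduled at ET, although they belong to the protocol's own routine safety set and laboratory change is a primary safety endpoint. For leavers whose stop was not triggered by a laboratory result, did not fall at a visit with both panels and had no unscheduled sample, the last scheduled value after Week 12 can be up to about 12 weeks old, or 16 weeks between Weeks 36 and 52. Up to about 20 to 24 weeks can separate it from the follow-up value. Before Week 12 the value is at most about 4 weeks old. These are worst cases on nominal days. The number of patients affected cannot be derived, because the documents give no expected discontinuation rate or timing. Adverse event collection is unaffected. This is a cheap correction that should be made, and it does not threaten the study's conclusions.

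The unspecified reference for safety and PD change is a secondary request for clarification only.

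**What to change.** Mark Hematology and Chemistry in the ET column of Appendix 1. The cost is a small extra blood volume at a visit where blood is already taken. Two limits remain. Section 4.5.1 does not tie ET to the last dose, so the sample may fall some days after stopping, and patients who withdraw consent may not be reached.

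As an optional clarification, state in Sections 6.4 and 6.7 which value is the reference for safety and PD change. For patients from GDC-0853 arms, the sponsor could show change from the GA29350 pre-dose baseline beside change from Day 84. This needs a merge with parent-study data, which the ACR50 analysis already requires and which is eased by patients keeping the same number. The cost is one more column in the displays.

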4.5.2 Study Treatment Discontinuation

Patients must discontinue study treatment if they experience any of the following:

- Pregnancy
- Anaphylaxis or other severe hypersensitivity reaction

- Malignancy (with the exception of non-serious local and resectable basal or squamous cell carcinoma of the skin)
- Any serious infection or infection requiring treatment with an IV antimicrobial agent
- Any prohibited medication as defined in Section 4.3
- Any Grade 3 or greater thrombocytopenia (National Cancer Institute Common Terminology Criteria for Adverse Events [NCI CTCAE v4.0])
- Any Grade 4 neutropenia (NCI CTCAE v4.0)
- Failure to achieve a 20% improvement in both SJC and TJC (relative to baseline values in Study GA29350) at Week 24

Patients who discontinue study treatment prematurely for the reasons listed above will be asked to return to the clinic for an early termination visit (see Section 4.5.1) followed by 8 weeks of safety follow-up.

The primary reason for study treatment discontinuation should be documented on the appropriate eCRF. Patients who discontinue study treatment prematurely will not be replaced.

4.5.3 Study and Site Discontinuation

The Sponsor has the right to terminate this study at any time. Reasons for terminating the study may include but are not limited to the following:

- The incidence or severity of adverse events in this or other studies indicates a potential health hazard to patients.
- Patient enrollment is unsatisfactory.

The Sponsor will notify the investigator if the Sponsor decides to discontinue the study.

The Sponsor has the right to close a site at any time. Reasons for closing a site may include but are not limited to the following:

- Excessively slow recruitment
- Poor protocol adherence
- Inaccurate or incomplete data recording
- Non-compliance with the International Conference on Harmonisation (ICH) guideline for Good Clinical Practice
- No study activity (i.e., all patients have completed the study and all obligations have been fulfilled)

